* = Trend toward significance between groups I and II [(free Kappa, $P = 0.07$), Kappa/Cr, $P = 0.08$)]

Results suggest excretion of urinary polyclonal free light chains is increased in obese subjects with DM and hypertension as compared to normal controls.

Limitations of this data include the cross-sectional design and use of Ace Inh and/or ARB class of drugs by 75% of the subjects in groups II and III. Therefore, the effect of Ace Inh and/or ARBs on the mean change of UFCs as compared to UMACR could not be assessed.

Approach

The proposed research project is aimed at studying the effect of anti-hypertensive medications on UFCs as compared to UMACR. We will recruit subjects with CKD stages I, II, and III. This will allow us to have a direct comparison between the two variables (UFCs and UMACR) across the above three stages of CKD, excluding stages IV and V. The reason for excluding patients with stages IV and V is that decreased clearance of the UFCs will confound the results.

Inclusion Criteria:

- 1- Men and women with DM, type 1 or type 2.
- 2- Age 18- 75
- 3- Estimated glomerular filtration rate (eGFR) > 30 ml/min
- 4- Hypertension
- 5- Use of Ace Inh and ARB for control of blood pressure who are willing to be placed on alternate drug(s) in the washout period for blood pressure control.

[figure not shown]
Exclusion Criteria:

- 1- Pregnancy
- 2- Patients with chronic kidney disease stage with eGFR ≤ 30 ml/min (CKD stage IV and V)
- 3- Nephrotic range proteinuria (urinary protein > 3.5 gm/day)
- 4- History or renal transplantation
- 5- History of multiple myeloma
- 6- Known history of hypersensitivity reaction or intolerance to Ace Inh or ARB, Amlodipine, Terazosin, Hydrochlorothiazide, and/or Hydralazine.

Research Design

This is a prospective, interventional study involving patients with either type I or type 2 DM and hypertension, which will be recruited from the outpatient clinics and the Tulane volunteer registry. Patients who meet the inclusion criteria on evaluation of blood work in the last 90 days of the visit will then undergo screening.

Information from the most recent laboratory data will be collected. There will be no genetic testing. The study is designed to include patients with and without diabetic nephropathy. All pertinent medications will be recorded as this information will be very important in interpreting the results of the data analyses. Below is a schematic representation of the visit schedule.

Washout period

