In the washout period, if Ace Inh or ARB classes of drug are part of patients' antihypertensive regimen, then the Ace Inh and/or ARB medication(s) will be discontinued. The patient will be started on alternative therapy (Amlodipine, Hydralazine, Terazosin and/or Hydrochlorothiazide) for control of their blood pressure. **The goal for their blood pressure will be set at < 140/90 mm/Hg.**

Test Period

On day 1 of the test period, patients will be advised not to take their blood pressure medication(s) prior to the study visit. During the study visit, urine sample will be collected for analysis of spot UFCs and spot UMACR. Additional 40 ml of urine and 10 ml of blood will be collected and stored for further analysis. The stored urine will be analyzed for cystatin C, NGAL. Urine and blood will be analyzed for other markers of obesity, diabetes, cardiovascular and kidney disease depending on the availability of funding.

After the blood and urine sample have been collected in a fasting state, those patients that were on Ace Inh or ARB prior to the washout period, will be started on the same regimen (Ace Inh and/or ARB). The alternate medication(s) that were started during the washout period will be discontinued.

Amlodipine, Hydrochlorothiazide, Hydralazine, Terazosin, Lisinopril and Losartan are all available in generic formulations. The dose of the drug and the decision to titrate the medication(s) for appropriate control and/or addition of medications will be decided by the principal investigator.

Methodology

Urine samples collected from patients will be aliquotted and stored in a -70oC deep freezer until the assays are performed. The following assays will be used to measure the respective markers.

- 1- A new latex-enhanced immunonephelometric assay measuring free k and l light chains as a free form (Freelite®, The Binding Site, San Diego, CA) has been developed. We have measure urinary polyclonal k and l FLC of immunoglobulins by the nephelometric immunoassay.
- 2- Microalbuminuria[Micro-albumin (MAB) (Orgentec Diagnostic, Mainz, Germany], and urinary excretion of low molecular weight proteins, cystatin C (CSC) (Arbor Assays, Ann Arbor, MI) and NGAL (R&D Systems, Minneapolis, MN) will be quantified by competitive solid phase enzyme immunoassay (ELISA) in accordance with the manufacturer's instructions.
- 3- Urinary creatinine (CRN) levels will be measured by Jaffe's method.

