Patients will be recruited from the outpatient clinics and the Tulane volunteer registry. All patients will sign the informed consent prior to starting the study. **Data safety monitoring board** will be formed that will review the data every six months to ensure patient safety and recommend continuation or discontinuation in the study. All patient information and data will be stored in a safe place under lock and key.

The target of blood pressure for patients during the washout period of the study is < 140/90 mm/Hg as per treatment guidelines(10). It is important to change the medications, as Ace Inh and ARB are the first line therapy in patients with DM. Since the focus of the proposed project is to study the effect of Ace Inh and ARB on UFC, collection of UFC with Ace Inh and/or ARB will confound the results.

To address this, patients will be advised to check their blood pressure at least 3 times / week either at home or in a facility such as a pharmacy. Given the variability in the machines, they will be advised to be consistent about where they check their blood pressure. If the blood pressure is > 130/80 mm/Hg, they will be advised to contact the principal investigator. The principal investigator will then make appropriate changes to their medication regimen.

Significance

Inclusion of patients with many different clinical (DM and HTN, with and without nephropathy) and biochemical variables will allow us to evaluate the prevalence of these clinical and biochemical parameters, including albuminuria and relate it to the UFCs depending on the renal function. In those patients in whom UMACR < 30 upon entering the study, it will allow us to collect data on the effect of anti-hypertensive medications on UFCs before kidney damage starts as compared to UMACR. This cohort of patients can be followed over time to assess the utility of UFCs as a marker of kidney damage in comparison to UMACR. In those subjects, that do have established kidney damage (diagnosed by UMACR > 30); data collected at the end of the study will allow us to study the effect of anti-hypertensive medications on UFCs as compared to UMACR. The next step for this cohort of patients would be to follow them longitudinally to examine the role of UFCs as a prognostic marker of progression of kidney damage in comparison to UMACR. **Data from the proposed study will be used to apply for funding for a longitudinal study.**

Key Personnel

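### Does the 130/80 contact level conflict with the washout blood pressure goal of below 140/90?

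*Combined protocol and SAP*

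**What the plan says.** Under Washout period, patients on an ACE inhibitor or ARB stop it and move to one or more of four alternative drugs. The aim is then given: "The goal for their blood pressure will be set at < 140/90 mm/Hg". The section Subject recruitment and safety repeats this target and attributes it to treatment guidelines.

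The same section asks patients to check their blood pressure at least three times a week and adds: "If the blood pressure is > 130/80 mm/Hg, they will be advised to contact the principal investigator". The next sentence reads: "The principal investigator will then make appropriate changes to their medication regimen".

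Two further statements bear on the matter. Under Test Period, "the decision to titrate the medication(s) for appropriate control and/or addition of medications will be decided by the principal investigator". Under Research Design, "All pertinent medications will be recorded as this information will be very important in interpreting the results of the data analyses".

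On Day 1 of the test period patients are advised to hold their blood pressure drugs before the visit. Samples are then taken, the previous ACE inhibitor or ARB is restarted, and "The alternate medication(s) that were started during the washout period will be discontinued".

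**The concern.** Read literally, the two levels overlap. A patient whose pressure lies above 130/80 but below 140/90 has met the stated goal, yet must call an investigator who, the text says, will make changes. Nothing describes 130/80 as an early-warning level, as a home-reading equivalent of 140/90, or as a level for some other period or subgroup. The discretion clause under Test Period names neither level.

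Two things could be at stake. The first is safety: these patients have been taken off drugs that the protocol calls first line, and self-monitoring with a call is the only check between visits that the available text describes. The second is the data. The washout regimen precedes the Day 1 urine sample, which supplies the baseline for change in urinary free light chains (UFLC) and in the urine microalbumin:creatinine ratio (UMACR). If the level acted on varied from patient to patient, so would the treatment preceding baseline.

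**Working it through.** No figure in the plan depends on these levels, so the check is a comparison of the text.

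**1. The two rules applied to example readings.** Inputs: goal below 140/90 (Washout period; Subject recruitment and safety); contact above 130/80 (Subject recruitment and safety).

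| Reading | At goal? | Call? | Do the rules pull apart? |
|---|---|---|---|
| 128/78 | yes | no | no |
| 135/85 | yes | yes | only if the call must end in a change |
| 145/95 | no | yes | no |

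Band width: 140 − 130 = 10 mmHg systolic and 90 − 80 = 10 mmHg diastolic.

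**2. Is any patient above goal missed?** Take each level component by component: off goal means systolic at least 140 or diastolic at least 90, and a call is due if systolic exceeds 130 or diastolic exceeds 80. Since 140 > 130 and 90 > 80, every off-goal reading prompts a call. The text does not spell this reading out. If a call needed both components to be raised, while either one could put a patient off goal, a reading such as 145/78 would be off goal with no call. That pairing treats the two levels by different conventions, and nothing in the text suggests it.

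**3. What must follow the call?** The safety section promises changes that are appropriate. Test Period gives the principal investigator the decision to titrate or add drugs, with appropriate control as the purpose, and the goal is stated shortly before, under Washout period. Taken together, the patient calls at one level and the investigator judges what is appropriate against the goal. Both sections assign the decision to the same single role, so the text creates no second decision-maker who might apply a different level.

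**4. Could the gap alter the baseline values?** Washout treatment may be any one or more of four drugs. That gives 2⁴ − 1 = 15 possible combinations, before dose, which is also discretionary. Regimens before Day 1 will therefore differ between patients whatever is said about 130/80, and joining the two levels in one sentence would not make them uniform. The instruction to hold blood pressure drugs before the Day 1 visit does not undo earlier treatment, but it belongs in the account. Medications are recorded, and Statistical analysis provides for regression on covariates.

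**5. Does any planned figure use these levels?** Power and sample size rests on 150 patients, 80% power, alpha 0.05, a 30% reduction, a correlation of 0.7 and standard deviations of 72 and 17 mg/L. Blood pressure is not among them. Under Statistical analysis it is named only as a traditional marker to be correlated with cystatin C and NGAL, with no cut-point.

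**6. A related wording difference.** The Medicine paragraph of the budget names two of the four washout drugs. Both are on the Washout period list, so this is budget shorthand with no bearing on the levels.

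**The case for a change.** The strongest case for a change rests on the words that changes will be made. That phrase does not naturally mean that perhaps nothing is done, so a patient at 135/85 could reasonably be left alone by one reader and changed by another. The rule is applied repeatedly, at least three times a week, in patients without their usual therapy. The discretion clause does not mention either level. A sentence or two would settle it without touching visits, assays or sample size.

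Much of this is fair. The relation between the levels is unstated, and the stricter reading is available. It is also only by position in the text that the contact sentence appears to concern the washout period.

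What does not stand is the step from an unstated relation to a fault in the plan. A contact level below a treatment goal is coherent, since it can serve as a margin. The patient's own instruction is single and clear. The argument about baseline gives no size or direction of effect on UFLC or UMACR, and it attributes to the threshold a variation in regimen that the design allows anyway. Low cost alone does not make a clarification necessary.

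**Conclusion.** The concern does not call for a change. The quoted levels are correct and no sentence links them, but a goal and a lower contact level are not a contradiction. Followed as written, the contact rule misses no above-goal reading, and no planned figure or analysis uses either level. What is missing is an explanation of a band 10 mmHg wide in each component, which the principal investigator can supply in running the study.

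This rests on three assumptions: both levels are read component by component; the contact sentence applies to the washout period, at least among others; and appropriate changes leave room for judgement. How many patients fall in the band cannot be computed, because the documents give no blood pressure distribution. The visit schematic is not shown in the available text and was not assessed. Nothing here favours one level over the other; those values belong to the investigators.
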